### Hypothesis

We hypothesise that 10-days of overnight moderate hypoxia will:

1. Improve glucose control
2. Improve insulin sensitivity
3. Reduce appetite / food intake
4. Reduce body mass
5. Improve inflammatory status
6. Improve redox balance
7. Increase gut anaerobe content
  
8. Maintain habitual physical activity
9. Have no effect on sleep quality

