#### *Secondary outcome measures*

Fasting venous blood [glucose] peak venous blood [glucose] during OGTT, Homeostatic Model Assessment for Insulin Resistance (HOMA-IR), daily glucose excursions (continuous glucose monitoring), and untargeted metabolomics, body mass / composition change, hormonal markers of appetite (e.g. leptin and ghrelin), food intake, gut microbiome, markers of inflammatory status (e.g. interleukin-6; nitrite), redox balance (TNF $\alpha$ ; SOD), HIF-1 $\alpha$ , extracellular HSP70, physical activity and sleep quality.

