#### **Inclusion Criteria**

- 1) Males and females with T2DM (as diagnosed with the WHO criteria).
- 2) Ability to understand the study and provide informed consent.

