#### **Exclusion Criteria**

Individuals with contraindications to hypoxic exposure such as;

- 1) obstructive sleep apnoea,
- 2) extant cardiac conditions
- 3) on medications such as SGLT2 inhibitors or PPAR antagonists
- 4) glycated haemoglobin < 48
- 5) sickle anemia,
- 6) thalassemia,
- 7) haemoglobinopathy
- 8) FVC < 80% of predicted FVC
- 9) FEV1:FVC ratio < 5th percentile for age and sex (as according to the European Respiratory Society and American Thoracic Society guidelines) (37) .

,

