## 10.4 Study Assessments

### **OGTT**

Fasted blood samples will then be taken for the measurement of plasma glucose and insulin concentrations ([glucose] and [insulin], respectively), and these data will be used to calculate  $\beta$ -cell function via the HOMA-%B model. Following this, participants will consume 75 g of glucose, and blood samples will be taken at 0 and 120 minutes post-glucose ingestion for the assessment of plasma [glucose] and [insulin]. Utilising the data from the OGTT protocol, insulin sensitivity of those not on insulin will be estimated using Stumvoll's insulin sensitivity index [31].

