### **Continuous glucose monitoring (CGM)**

The sensors (Abbott Diabetes Care Inc., Alameda, CA, USA) will be fixed to the anterior portion of the upper arm with a small adhesive patch. These sensors will be worn for 14 days to determine free-living glycaemic control.

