### 12.3 Recording and Reporting Procedures for All Adverse Events

All adverse events will be recorded in participant file notes. Distinction between SAE and AE will be made by an independent medical officer. All SAE will be reported to the sponsor and the REC regardless of if it is related or not.

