### 14.2 Analysis of Endpoints

All data will be tested for normality using the Shapiro-Wilk test. For normally distributed data, paired samples t-tests will be used to assess differences pre and post hypoxic exposures for; blood [glucose] (AUC and peak), insulin sensitivity, eHSP70, IL-6, leptin, ghrelin, TNFa, SOD, HIF-1 $\alpha$  HR, PA and sleep efficiency. For non-parametric data Wilcoxon-Signed rank test will be used for pairwise comparisons. Repeated measures one-way analysis of variance (ANOVA) will be used to identify differences between conditions for SpO2 and [glucose] across time from the CGMs. Mauchly's test of sphericity will be used to determine if any data violated the assumption of spherical data. If violated, sphericity will be accounted for using the Greenhouse-Geisser correction. Where significant differences are observed ( $P < 0.05$ ), post-hoc tests will be performed using LSD pairwise comparisons. Effect sizes will be reported as partial eta squared ( $\eta^2_p$ ) (small = 0.01; medium = 0.06; large = 0.14) [33].

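### The planned CGM analysis compares glucose level only, so low readings seen only on the sensor would not be reported as a safety result, although insulin users appear eligible

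*Combined protocol and SAP*

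**What the plan says.** **Who can enter.** The disease criterion for inclusion in section 8.3 is "Males and females with T2DM (as diagnosed with the WHO criteria", with no restriction by glucose-lowering treatment. The drug exclusion covers people "on medications such as SGLT2 inhibitors or PPAR antagonists"; insulin is not named. The OGTT text in section 10.4 says that "insulin sensitivity of those not on insulin will be estimated" with a particular index, which implies that some participants may be on insulin.

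**What the treatment is meant to do.** The first hypothesis in section 6 is "Improve glucose control". The exposure is overnight and at home.

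**What the CGM is for.** Section 7.2 lists "daily glucose excursions (continuous glucose monitoring" as a secondary outcome without defining it. Section 10.4 gives the purpose: "These sensors will be worn for 14 days to determine free-living glycaemic control". The Intervention text in section 10 treats SpO2 as the safety recording and mentions the CGM as something additional. The only alarm described is for SpO2.

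**How the CGM is analysed.** Section 14.2 names a repeated-measures one-way ANOVA to identify "differences between conditions for SpO 2 and [glucose] across time from the CGMs". Section 14.4 says that no further SAP is needed for this pilot.

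**How harms are captured.** Section 12.3 states: "All adverse events will be recorded in participant file notes". An independent medical officer separates serious from non-serious events, and all serious events go to the sponsor and the ethics committee. Section 14.2 plans no summary of adverse events by condition.

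**The concern.** An intervention intended to improve glucose control, tested in a sample that may include insulin users, can lower recorded glucose in two ways. High values may come down, which is the hoped-for benefit, or more values may become low, which is a possible harm. The planned comparison responds to both in the same direction. Nothing in the supplied text mentions hypoglycaemia, a low-glucose level or time below such a level, whether under outcomes, analysis, safety or the listed risks.

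Two things are at stake. First, the trial collects overnight glucose data but plans no statement on whether low readings were more frequent under hypoxia. Second, a lower CGM glucose could be taken as support for the first hypothesis when part of it reflects more lows. Section 20 says the pilot's results will be used to define the primary outcome of a definitive trial and to power it, so a safety result would be useful there.

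**Working it through.** The plan states no figure on this point, so there is none to reproduce. The check has four steps.

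**1. Can insulin users be in the sample?** Inclusion is open to T2DM generally, insulin is not among the named exclusions, and one index is confined to participants not on insulin. That restriction has a purpose only if some participants use insulin. The exclusion list is worded as examples, so this is a strong inference and not an explicit statement.

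**2. Can the planned analysis tell the two kinds of fall apart?** If a share *h* of readings drops from an average *a* to a low value *b* and all other readings stay the same, then

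change in mean = −*h* × (*a* − *b*).

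The values here are assumed, not taken from the documents: a simulated trace with mean about 9.0 mmol/L, in which some readings between 4 and 8 mmol/L (averaging about 6.4) move to 3.2 mmol/L. Then *a* − *b* = 6.4 − 3.2 = 3.2 mmol/L.

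| Share of readings that become low | Change in mean glucose (mmol/L) | Time above 10 mmol/L |
|---|---|---|
| 1% | −0.01 × 3.2 = −0.03 | unchanged, about 34% |
| 4% | −0.04 × 3.2 = −0.13 | unchanged, about 34% |
| 10% | −0.10 × 3.2 = −0.32 | unchanged, about 34% |
| 15% | −0.15 × 3.2 = −0.48 | unchanged, about 34% |

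Glucose level falls with no reduction in high glucose. The table shows direction and sensitivity. It does not estimate what will happen in this trial.

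**3. Does analysing across time solve this?** It could show when a fall occurs, depending on the time unit, which 14.2 does not give. It would not show that an individual was low, because the comparison is of group means. With assumed values, one participant at 3 mmol/L and 22 at 9 mmol/L average (3 + 22 × 9)/23 = 201/23 = 8.74 mmol/L. That is 0.26 below 9 and gives no sign of a low reading.

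**4. Do other parts of the plan close the gap?** Section 12.3 would record a low that someone notices and reports. It has no rule that turns a CGM reading into an event. Section 11.4 records medication but does not link it to glucose. Section 14.1 analyses only participants who complete all visits, and section 16.2 states that there is no steering or data monitoring committee. What remains uncovered is lows seen only on the sensor.

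**Availability of the data.** The Intervention text in section 10 has the CGM worn during the exposure, for 14 days. The text on visits 2 to 5 has a new sensor fitted at visit 3, followed by a 4-week washout before visit 4. Read literally, that sensor ends 28 − 14 = 14 days before the earliest visit 4. The supplied text does not show which sensor covers the second exposure, and the flow figure that might do so is not shown.

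**The case against.** The strongest reply is that the plan is less exposed than it looks.

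- **Adverse events.** A reader might infer that a glucose-lowering harm would appear nowhere as a harm. The documents do not support that. Section 12.3 records all adverse events, and section 12 counts important medical events as potentially serious. A symptomatic or treated low would be captured. This stands, and it confines the gap to lows seen only on CGM.
- **Direction.** A reader might infer that lows would be scored as improvement. Section 14.2 tests for differences and states no rule that lower is better. That reading comes from the first hypothesis. It is a risk in interpretation, not a planned scoring rule.
- **Excursions.** The secondary outcome on daily excursions could include downward ones. It could, but it is undefined and 14.2 gives it no analysis other than glucose level. Defining it would be a natural place for part of the fix.
- **Size.** A single-person scenario gives larger figures: 2 hours a night at 3 instead of 8 mmol/L lowers the daily mean by (8 − 3) × 2/24 = 0.42 mmol/L and an 8-hour night mean by (8 − 3) × 2/8 = 1.25 mmol/L. Section 14.2 names neither mean, and the scenario is assumed, so these do not measure the effect on the planned analysis. The documents give no rate of lows. People with glycated haemoglobin below 48 are excluded, and the distortion is small if lows are rare.
- **Consequence.** The primary endpoint is the OGTT glucose AUC, which this analysis does not enter. Section 20 speaks of the pilot's results in general, not of CGM.

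These points limit the claim. They do not supply a planned low-glucose result.

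**Conclusion.** The point holds in a limited form. As written, the CGM analysis cannot separate a reduction in high glucose from an increase in low glucose. Lows seen only on the sensor would not be reported as a safety result, and a lower CGM glucose could be read as support for the first hypothesis.

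This rests on two readings of the text: that insulin users are eligible, which is inferred, and that the glucose comparison in 14.2 is the only planned CGM analysis, which the supplied text supports. The size cannot be stated, because the documents give neither the share of participants on insulin nor the frequency of lows. The documents do not support saying that harm would be hidden altogether or that the primary result is at risk. This is an inexpensive improvement to safety reporting and does not challenge the main analysis.

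**What to change.** 1. In 14.2, pre-specify a descriptive CGM safety summary by condition over the 10 exposure nights: percent of time, and number of nights with any reading, below a low-glucose level that the sponsor states in advance. Report it beside the CGM glucose comparison, with the paired difference and its confidence interval.
2. List individual values by use of insulin or other glucose-lowering drugs, from the 11.4 medication record, without subgroup tests. Include recorded nights from participants who do not complete all visits, whom 14.1 would otherwise leave out.
3. Do not make a claim of improved control conditional on time below the level being no higher under hypoxia. Such a rule has no margin. With no true difference and few ties, chance would block the claim about half the time.
4. Reconcile the two descriptions of CGM timing in section 10, so that it is clear that both exposure periods have CGM data.

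The cost is a small amount of extra analysis of CGM files and a medication record already planned, provided item 4 confirms data in both periods. The downside is low precision: with at most 23 participants the interval may be wide, and it should be presented as descriptive.

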Study Design	Single blind, randomized, balanced, crossover design study (i.e. participants will undergo both the hypoxia and sham conditions and will be blinded to the conditions in which they are in).
Study Participants	Individuals with type 2 diabetes
Planned Sample Size	The study of 23 subjects provides adequate power (including a 15% drop-out rate typically seen in our clinical trials): 13 subjects are required to detect a 1 standard deviation change [30] in venous blood [glucose] during a 2 hour oral glucose tolerance test (OGTT (alpha = 0.05; power = 80%)).
Follow-up duration	1 months washout – 10 day intervention
Planned Study Period	1 year
Primary Objective	Post-intervention (sham vs hypoxia) area under curve for venous blood [glucose] during a 2 hour OGTT.
Secondary Objectives	Fasting venous blood [glucose], peak venous blood [glucose] during OGTT, Homeostatic Model Assessment for Insulin Resistance (HOMA-IR), daily glucose excursions (continuous glucose monitoring), and untargeted metabolomics, body mass / composition change, hormonal markers of appetite (e.g. leptin and ghrelin), food intake, gut microbiome, markers of inflammatory status (e.g. interleukin-6; nitrite), redox balance (TNF $\alpha$ ; SOD), HIF-1 $\alpha$ , extracellular HSP70, physical activity and sleep quality.
Primary Endpoint	Post-intervention (sham vs hypoxia) area under curve for venous blood [glucose] during a 2 hour OGTT.
Secondary Endpoints	See secondary objectives.
Intervention (s)	10 days of moderate home-based overnight normobaric hypoxia (F 1 O 2 = ~0.155, or sham hypoxia intervention (F 1 O 2 = 0.2093) using hypoxic ‘pillow tents’.

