## **20. DISSEMINATION AND OUTCOME**

Results (estimates of effect sizes and confidence intervals) from this pilot study will be utilised to define our primary outcome and to power a larger, definitive multi-centre randomised control trial with our co-applicants and collaborators around Europe. Once our final report has been submitted to the funder, we will apply for NIHR funding via a researcher-led Research for Patient Benefit (RfPB) or an Efficacy and Mechanism Evaluation (EME) bid (depending on the effect size and sample size). The results will be disseminated through publication in peer-reviewed scientific and clinical journals and via presentations, local, national and international meetings. A summary of the results will be sent to all the participants. Finally, an open day and presentation will be carried out where the participants will be informed of the study findings and have the opportunity to ask any pertinent questions and/or provide feedback.

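### Partial eta squared, the only effect measure named in section 14.2, does not supply what section 20 needs to define and power the definitive trial

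*Combined protocol and SAP*

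**What the plan says.** Section 14.2 gives two families of tests. For glucose AUC and peak, insulin sensitivity and a list of biomarkers and behavioural measures, "paired samples t-tests will be used to assess differences pre and post hypoxic exposures", with a Wilcoxon alternative. For the remaining outcomes, the plan is "Repeated measures one-way analysis of variance (ANOVA) will be used to identify differences between conditions for SpO 2 and [glucose] across time"; glucose here means sensor glucose. Sphericity corrections and post-hoc comparisons follow. The section closes with "Effect sizes will be reported as partial eta squared" and the labels "small = 0.01; medium = 0.06; large = 0.14". No mean difference, SD, correlation or confidence interval is specified, and section 14.4 states that no further SAP is needed.

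Section 20 says what the pilot is for. Its effect-size estimates and confidence intervals, according to that section, "will be utilised to define our primary outcome and to power a larger, definitive multi-centre randomised control trial". The choice of funding scheme is also made "depending on the effect size and sample size".

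**The concern.** The pilot's stated product is the input to a larger trial, so the effect measure is a main deliverable. Partial eta squared suits that use poorly.

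- It has no sign, so benefit and harm of equal size look the same.
- It has no units, so it cannot be set against a clinically relevant change in glucose.
- It is biased upwards when the sample is small.
- It mixes the mean change with the within-person correlation and reveals neither the SD nor the correlation.
- It does not come from the Wilcoxon test that section 14.2 allows.

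Two consequences follow. Labels fixed in advance may describe noise as a medium or large effect. And because section 20 lets the results define the next primary outcome without saying how, that outcome could be a chance finding.

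**Working it through.** **Inputs.** The Synopsis states "The study of 23 subjects provides adequate power (including a 15% drop-out rate typically seen in our clinical trials"): 23 × 0.85 = 19.55, so about 19 completers, and section 14.1 analyses completers only. Section 9 gives 20 enrolled instead: 20 × 0.85 = 17. The cut-offs are from section 14.2.

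**The plan's own figure.** The plan needs 13 subjects for a 1 SD change (alpha 0.05, power 80%). Taking the SD as that of paired differences, a two-sided paired t-test needs 10 (power 80.3%), and 13 gives 91.1%. The 13 is not reproduced on that reading, but the type of SD is not stated and nothing below depends on it.

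**Formula.** For a paired t-test, partial eta squared = t²/(t² + n − 1). At cut-off c and n = 19, t = √[18c/(1 − c)] and the paired standardised difference is dz = t/√19. For c = 0.14: t = √(2.52/0.86) = 1.71 and dz = 1.71/4.36 = 0.39. With no true effect the statistic follows a Beta(1/2, 9) distribution with mean 1/19 = 0.053, just under the 'medium' cut-off.

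| Cut-off | t | dz | Chance of passing with no effect |
|---|---|---|---|
| 0.01 (small) | 0.43 | 0.10 | 67% |
| 0.06 (medium) | 1.07 | 0.25 | 30% |
| 0.14 (large) | 1.71 | 0.39 | 10% |

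With 17 completers the chances are 69%, 33% and 13%; with all 23 they are 64%, 25% and 7%.

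**What 'large' means.** At n = 19, p < 0.05 needs t = 2.10, that is 4.41/(4.41 + 18) = 0.197. A value of 0.14 has p = 0.10, and the 95% interval for dz runs from −0.08 to 0.86. The 1 SD planning effect, read as an SD of paired differences, gives 19/(19 + 18) = 0.51.

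**ANOVA outcomes.** The number of levels k is not given. Assuming sphericity and n = 19, a null effect reaches 'large' in 7% (k = 3), 4% (k = 4) or 0.1% (k = 14) of cases, but still reaches 'medium' in 32% to 34%.

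**Carrying 0.14 forward.** For another paired study (two-sided 0.05, 80% power) dz = 0.39 gives 53 people. For a parallel-group trial the correlation ρ is also needed: d² = dz² × 2(1 − ρ), with dz² = 0.1542, and n per arm = 2(1.96 + 0.84)²/d² ≈ 15.70/d². Assumed correlations of 0.3, 0.5 and 0.7 give 15.70/0.2159 = 73, 15.70/0.1542 = 102 and 15.70/0.0925 = 170 per arm.

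**Selection.** Section 14.2 lists 13 paired outcomes. If all were null and independent, the chance that at least one is 'large' is 1 − (1 − 0.104)^13 = 76%. Simulation with a between-outcome correlation of 0.3 gives 68%. If only a favourable direction counted, the independent figure falls to 1 − (1 − 0.052)^13 = 50%.

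**The case against.** The strongest objection concerns scope. The eta-squared sentence ends a run of text on repeated-measures ANOVA, where the statistic belongs, and may cover only oxygen saturation and sensor glucose. The paired-test figures would then not apply. This stands as a real ambiguity, but that reading leaves glucose AUC with no stated effect measure, so section 14.2 needs the same repair.

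Second, section 20 does promise confidence intervals and never names partial eta squared. A reader might infer that eta squared alone will be handed on and that SDs will go unreported. The documents do not say so; they show only that section 14.2 does not specify these quantities, nor what the intervals are for.

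Third, a reader might infer that the outcome with the largest effect will become the next primary outcome. No such rule is stated. The 68% to 76% figure is a worst case that ignores direction and counts unlikely candidates: heart rate is not a listed outcome in section 7.2, and the hypotheses in section 6 expect activity to be maintained and sleep unaffected.

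Fourth, it would be too strong to say that the measure cannot be carried forward. With n known, the absolute paired difference can be recovered and a paired study sized from it. What cannot be recovered is direction, units, SD and correlation; the correlation matters if the next trial is parallel-group, which section 20 does not state.

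Last, a 'large' label at 0.14 would sit beside p = 0.10, and section 14.2 keeps P < 0.05 as its criterion. That limits the harm within this report, but not when effect sizes are used for planning.

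**Conclusion.** The point holds as a mismatch between sections 14.2 and 20. The one effect measure named is unsigned, unitless and upward-biased, and the quantities needed to size the next trial are not specified. On the paired-test reading with 19 completers, a null outcome is labelled 'medium' or above about 30% of the time and 'large' about 10%. So 'often' is fair for 'medium' but not for 'large' on a single outcome. On the ANOVA-only reading, the gap is that the primary endpoint has no effect measure. The open route to a data-driven primary outcome is a genuine weakness, but its size depends on a selection rule that the plan does not give. The current trial's hypothesis tests are unaffected. The change should be made because it corrects the pilot's main product at little cost.

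**What to change.** In section 14.2, for each paired outcome, report the within-person mean difference for the planned contrast in original units with a 95% confidence interval, including hypoxia versus sham for the primary endpoint. Add the between-person SD, the SD of differences and the within-person correlation. Drop the small, medium and large labels.

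In section 20, state that the definitive trial's primary outcome and target difference will be chosen on clinical grounds, and that the pilot will supply variability, correlation and retention rather than the observed effect size.

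The cost is wording only, from data already planned. The labels are lost and the next trial's size may look less favourable. The pilot will still be imprecise: with 19 completers the confidence interval half-width is 2.10/√19 = 0.48 SDs of the differences. That SD is known only to within about 0.76 to 1.48 times its estimate, so a sample size built on it could vary from about 0.57 to 2.2 times. The reported intervals would make this visible.
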